Screened Subject	Any subject who signed the study specific informed consent and completed at least one study-related procedure.
Screen Failures	Any subject who signed the study specific informed consent but either failed to meet study requirements during screening or met study requirements at screening, but was not enrolled.
Study Drug	Term used for study drug provided by the Sponsor (ESL, ie, Aptiom).
Treatment Period	The period of the study in which the study drug is administered.
Enrolled Subject	Any subject who was successfully screened and enrolled into the titration period of the study.
Completed Subject	Any subject who completed all the Schedule of Assessments up to and including assessments for the end of the Maintenance Phase (Visit 9, the end of the study).
Early Termination Subject	Any subject who was successfully screened and entered the treatment period of the study, but did not complete the study.
End of Study	The day that the subject completes the study per the study design (end of the Maintenance Phase, Visit 9).

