10.1.1. Treatment with Study Drug

Eligible subjects will begin the 2-week Titration Phase on Day 1 (Week 1), during which they will initiate treatment with ESL 400 mg/day and remain on that dose for 1 week (Days 1 - 7). Subjects will titrate to ESL 800 mg/day the beginning of week 2 (Day 8) and will remain on that dose for 1 week up to the beginning of the maintenance phase. Subjects will maintain a minimum dose of 800 mg/day for the Maintenance Phase; however, during the Maintenance Phase, subjects may titrate in weekly increments of 400 mg/day as medically indicated at the discretion of the Investigator up to a maximum dose of 1200 mg/day (Canadian sites) or 1600 mg/day (US sites) (based on maximum local labelled dose).

During the 24-week Maintenance Phase, only one reduction to a minimum of 800 mg/day is permitted. Subjects requiring doses < 800 mg/day will be discontinued from the study.

Subjects who complete the 24-week Maintenance Phase may choose to continue treatment with commercial ESL. Subjects who chose not to continue treatment with ESL for any reason will be gradually tapered off drug unless abrupt discontinuation of the drug is required in response to an AE. The taper schedule is provided in Table 5.

Table 5: Taper of Study Drug

Dose (mg/day)	First Week	Second Week	Third Week
800	400	Stop	Stop
1200	800	400	Stop
1600	800	400	Stop

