10.1.2. Premature Discontinuation of Treatment with Study Drug

Subjects who prematurely discontinue treatment with ESL prior to Visit 9 (EOS) for any reason will be gradually tapered off study drug (see Table 5). However, abrupt discontinuation of the drug is permitted for the treatment of an AE. Subjects who prematurely discontinue treatment with ESL (abruptly, or by taper) will be withdrawn from the study.

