15.3.6. Efficacy Analyses

All efficacy endpoints will be summarized descriptively in this study. Changes in efficacy parameters will be calculated with reference to the baseline, defined as the seizure data for the longest available period up to 3 months prior to screening from seizure history and from screening to first dose of study medication from the paper seizure diary.

All seizure related endpoints will be calculated based on the data from the paper diary.

Seizure frequency will be standardized to 28-day rate. The SSF and changes from baseline will be summarized during the first 12 weeks, the last 12 weeks, and the 24 weeks of the Maintenance Phase.

Two responder rates (50%, and 75% responder rates) are defined as subjects who have $\geq 50\%$, and subjects who have $\geq 75\%$ reduction in SSF from baseline, respectively. The proportions of

responders in each rate will be summarized during the first 12 weeks, the last 12 weeks, and the 24 weeks of the Maintenance Phase.

Relative reduction (%) in SSF from baseline will be calculated during the first 12 weeks, the last 12 weeks, and the 24 weeks of the Maintenance Phase.

The proportion (%) of seizure-free subjects will be provided during the first 12 weeks, the last 12 weeks, and the 24 weeks of the Maintenance Phase.

Time on ESL will be calculated from the first dose to the last known dose of ESL. The median time and 95% CI will be estimated using Kaplan Meier time to event methods. Subjects who were still on ESL at the end of study will be censored at the end of study. Subjects who dropped out of the study while receiving treatment will be an event at the time of the dropout. Change in dosage levels during the treatment period will be ignored.

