3.1. General Description

This is a 31-week, multicenter, 2-arm, prospective, open-label, non-randomized, Phase 4 study of ESL as adjunctive therapy in adult subjects with a diagnosis of epilepsy with POS. Two groups of ESL-naïve subjects will be evaluated. The groups are defined as follows:

Arm 1 (ESL as first add-on): This group will include subjects who have been maintained on a regimen consisting of a stable dose of LEV or LTG for at least 1 month (28 days) prior to screening and who have not used any adjunctive treatment.

Arm 2 (ESL as later add-on): This group will include subjects who have been maintained on a regimen consisting of a stable dose of 1 - 2 anti-epileptic drugs (AEDs) (excluding oxcarbazepine [OXC]) for at least 1 month (28 days) prior to screening and who have used adjunctive treatment in the past.

The Arm 1 subjects will allow an assessment of the efficacy and safety of ESL in subjects who are early in the course of their disease and being treated with one of the most common first line AEDs. The subjects in Arm 2 are similar to the subject population in the Phase 3 adjunctive studies, treatment-resistant subjects who are later in the course of their disease. The inclusion of these subjects in the present study will provide an assessment of the efficacy and safety of ESL as a later adjunctive therapy in a real world clinical setting. In addition, this study will provide data from both Arm 1 and Arm 2 for several behavioral, mood-related, and QOL-related assessments that were not evaluated in the Phase 3 program.

Approximately 100 subjects will be enrolled (approximately 50 subjects in Arm 1 and 50 subjects in Arm 2).

The study will consist of a Screening Phase of 1 to 2 weeks, followed by a 2-week Titration Phase, a 24-week Maintenance Phase, and a Safety Follow-up/Taper Phase of 4 weeks. The last visit in the Maintenance Phase (Visit 9) is considered the End of Study (EOS) visit.

The screening visit should take place 7 - 10 days prior to the titration visit and may be extended to 7 - 17 days if required with consent of medical monitor. Subjects of Asian ancestry who require HLA-B*1502 testing (eg do not have prior test results) may have the screening visit 7 - 17 days prior to the titration visit.

Subjects who withdraw prior to the EOS visit should have an Early Discontinuation Visit (EDV) within 72 hours.

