15.2.1.5. Time on ESL

Time on ESL will be calculated from the first dose as indicated in the Study Drug Dispensation source to the last known dose of ESL in the Disposition source. Subjects who were still on ESL at the end of study will be censored at the end of study. Subjects who dropped out of the study

while receiving treatment will be an event at the time of the last dose date. Change in dosage levels during the treatment period will be ignored.

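### Time on ESL: dropouts run to the last dose while completers are censored at Visit 9, so if taper doses count, a late leaver can force the Kaplan-Meier curve to zero and produce a spurious median

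*SAP*

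**What the plan says.** SAP 15.2.1.5 runs Time on ESL from first dose to the last known dose recorded in the Disposition source. Dropouts "while receiving treatment will be an event at the time of the last dose date". For the rest: "Subjects who were still on ESL at the end of study will be censored at the end of study". The protocol's table of key study terms and SAP 3.1 both place end of study at Visit 9. SAP 15.2.2.6 reports a Kaplan-Meier median with 95% CI and plots, and does not stop the curve at Visit 9.

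Protocol 15.3.6 uses two anchors in one paragraph. It also measures time to the last known dose, but then states: "Subjects who dropped out of the study while receiving treatment will be an event at the time of the dropout". SAP 3.4.2, which lists departures from the protocol's analyses, mentions only the dropped dose count and average daily dose.

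On tapering, Protocol 10.1.2 says: "Subjects who prematurely discontinue treatment with ESL prior to Visit 9 (EOS) for any reason will be gradually tapered off study drug", with an exception for an abrupt stop because of an adverse event. Under Protocol Table 5, the taper lasts one week from 800 mg/day and two weeks from 1200 or 1600 mg/day.

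**The concern.** Events and censoring may run on different clocks. Completers stop contributing at Visit 9, even if they keep taking ESL or taper afterwards. Dropouts may contribute until the end of a taper taken after they have left.

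This has two consequences. Each tapered dropout's event is one or two weeks late, which lifts the curve slightly. More seriously, when the longest observation in an arm is an event, the Kaplan-Meier estimate is 0 at that point, however many subjects completed. The report could then show a median of about 26 to 28 weeks for an arm in which most subjects were still on drug at Visit 9. Time on ESL is a listed efficacy endpoint and the natural companion to the retention rate, so the two results would appear to disagree.

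**Working it through.** **Inputs.** Time is counted in days after first dose.
- Visit 9 (SAP 3.1): 2 + 24 weeks = 26 × 7 = 182 days. The ±3-day window gives 179 to 185.
- Taper lag (Protocol Table 5): 7 or 14 days.
- Completion (SAP 3.3): 60% in Arm 1 and 50% in Arm 2, with about 50 subjects per arm. The protocol has 93 and 97.

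**The plan's own figures.** None is given for Time on ESL. The inputs it depends on reproduce:
- Protocol: 1.96² × 0.6 × 0.4 / 0.10² = 92.2, so 93; and 1.96² × 0.5 × 0.5 / 0.10² = 96.04, so 97.
- SAP, at 50 per arm: 1.96 × √(0.24/50) = 0.136 and 1.96 × √(0.25/50) = 0.139. These match its figure of about 14%, as a half-width.

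**Worked example.** Take 50 subjects: 30 completers, 19 dropouts whose last dose falls before the Visit 9 window, and one who leaves on day 177.
- Event at dropout: S = 30/50 = 0.60; median not reached.
- Event at last taper dose: before the final event, S = 31/50 = 0.62, already above observed retention.
- 14-day taper: the event is on day 177 + 14 = 191, after the last possible in-window Visit 9 (185). One subject is at risk, so S = 0.62 × (1 − 1/1) = 0 and the median is 191 days.
- 7-day taper: the event is on day 184. If all completers were censored on exactly day 182, S again falls to 0 and the median is 184. If visits are spread over the window and 8 completers remain at risk, S = 0.62 × (1 − 1/9) = 0.551 and the median is not reached.

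**Who is exposed.** To fall after a completer censored on day 185, the leaver must go after day 185 − 14 = 171 (14-day taper) or 185 − 7 = 178 (7-day taper). The Visit 9 window opens on day 179. That leaves about 8 days for the long taper and about 1 day for the short one, or a few days if the latest completer's visit is earlier than day 185.

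**Frequency.** This was simulated with assumptions that are not in the documents: constant or front-loaded dropout (Weibull shape 1.0 or 0.6), taper in half or all of dropouts, and Visit 9 spread over its window. For 50 subjects at 60% completion:
- Curve ends at 0: 9–63% if late leavers count as dropouts. If those leaving once the window opens instead have Visit 9, it is 3–8% for 7-day tapers and about 20–49% for 14-day tapers. With dropout dating it is 0%.
- Finite median: about 14–68% across these settings, against about 8–12% with dropout dating. The comparison figure is close to the chance that at least half the arm truly leaves: P(X ≥ 25), X ~ Bin(50, 0.4), = 9.8%.
- For 50% completion, a finite median is already expected in about 51–57% of arms with dropout dating; P(X ≥ 25), X ~ Bin(50, 0.5), is about 56%.
- At the protocol's 93 subjects and 60% completion, a separate run with other dropout and taper mixes, late leavers counted as dropouts, gave a curve ending at 0 in 20–79% of arms. More subjects means more late leavers.

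**The case against.** The strongest objection is that everything rests on the Disposition last-dose date including taper doses, and no section says that it does. At the early discontinuation visit, unused drug is collected and taper drug dispensed. The schedule of assessments does not mark ESL dose changes at that visit or at follow-up, and SAP 3.4.2 says accountability data were not collected. No scheduled step clearly records the end of a taper. The exposure bands beyond Week 27 (SAP 14) point the other way: a last dose at Visit 9, even 3 days late, gives 186 days or 26.6 weeks. But those bands follow the visit weeks, and a missing last dose is replaced there by last contact, so they do not settle it. This objection stands. If the field holds the last pre-taper dose, the problem disappears.

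A reader might infer that the SAP overrides a clear protocol rule. It does not: Protocol 15.3.6 also runs the measure to the last known dose, so the protocol itself leaves the event date open.

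A reader might also infer that anyone leaving in the final two weeks has an event after all completers. That is roughly right for 14-day tapers only, and a subject stopped abruptly has no lag.

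Finally, the endpoint is descriptive, there is no testing (SAP 6.6), and a terminal drop would be visible on the planned plot. That limits the harm, but the tabulated median and its interval would still mislead.

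**Conclusion.** The point holds conditionally. As written, the SAP lets dropout events fall after Visit 9 while completers cannot be followed past it, and neither document says whether taper doses count. If they do, the artefact is real and mainly a risk with 14-day tapers. Its frequency cannot be fixed from the documents; the span of 3–63% for a curve ending at 0 reflects the assumptions, not sampling error. In Arm 2 the median is less diagnostic, because a finite one is expected in about half of arms anyway.

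The documents do not support reading this as a threat to the primary result. Retention is a separate proportion with an exact interval (SAP 15.1) and uses no dose dates. This is a cheap correction to a secondary endpoint, not a flaw in the main conclusion.

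**What to change.** In SAP 15.2.1.5:
1. Use one event date for dropouts: the date of study discontinuation, in line with the dropout anchor in Protocol 15.3.6. Taper doses do not count. Do not offer the early discontinuation visit as an alternative, since it may follow withdrawal by up to 72 hours.
2. Censor completers at Visit 9 and cap the curve there, so that no event can fall later.
3. Report the median as not reached where that applies.
4. State the rule in SAP 3.4.2, because the protocol's two anchors are being resolved.
5. Keep the taper-inclusive last dose for the exposure table only, and say whether the Disposition field includes taper.

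This changes analysis dating only, not how subjects are tapered. The cost is a few lines of SAP text and a check that the discontinuation date is held in the disposition data. The downside is that Time on ESL no longer counts taper days and so departs from the last-known-dose wording in both documents.

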15.2.2. Analysis of Efficacy Variables

The efficacy analyses using paper seizure data will be performed for the mITT and PP populations, and the listings of subjects will be provided.

Time on ESL analysis will be performed for the safety population only.

15.2.2.2. Standard Seizure Frequency (SSF)

The SSF will be summarized using descriptive statistics for baseline, titration, each visit intervals between Visit 3 and Visit 9, the first 12 weeks, the last 12 weeks, and the 24 weeks of the Maintenance Phase.

Additionally, the SSF will be summarized by the subgroups presented in Section 15.3.

15.2.2.3. Responder Rates

The responder rates (50% and 75%) along with 95% confidence intervals (CIs) (using the exact method) will be presented for baseline, titration, each visit intervals between Visit 3 and Visit 9.

Additionally, the number and percentage of subjects with the subgroups presented in Section 15.3 will also be presented.

15.2.2.4. Relative Reduction in SSF

Relative (%) change in SSF from baseline will be summarized using descriptive statistics for baseline, titration, each visit intervals between Visit 3 and Visit 9, the first 12 weeks, the last 12 weeks, and the 24 of the Maintenance Phase.

The number and percentage of subjects with the subgroups presented in Section 15.3 will also be presented.

15.2.2.5. Proportion of Seizure-Free Subjects

The number and proportion (%) of subject's seizure-free along with 95% confidence intervals (using the exact method) will be summarized for baseline, titration, each visit intervals between Visit 3 and Visit 9.

Additionally, the proportion of seizure free subjects will be summarized with the subgroups presented in Section 15.3.

15.2.2.6. Time on ESL

The median time on ESL in days and 95% CI will be estimated using Kaplan Meier time to event methods.

Kaplan Meier plots for the time on ESL will be provided.

15.3. Subgroup Analysis of Efficacy Variable(s)

Standardized seizure frequency (SSF), and relative change (%) from baseline in SSF, will be summarized for mITT population, by the following subgroup variables which are defined in section 7.4.

- Number of baseline AEDs
- Baseline AEDs.
- Seizure Type

Responders, and proportion of seizure-free will be summarized by number of baseline AEDs and baseline AEDs.

15.4. Exploratory Variables

15.4.1. Analysis of Exploratory Variables

The exploratory analyses will be performed for the mITT populations.

The proportions of concordance in the daily seizure frequency during the 24-weeks of the Maintenance Phase between the watch device and paper diary as well as between the Mate application and paper seizure diary for each subject will be calculated. Proportion is calculated as the number of days with concordance in daily seizure frequency between the two Empatica devices and paper seizure diary divided by the number of days with seizure frequency available in paper diary. The mean and 95% CI (exact method) of the proportion of the concordance will be provided.

In addition, the proportion of concordance in daily seizure frequency during the 24-weeks of the Maintenance Phase between the Mate application and paper seizure diary will be calculated only with the subjects who confirmed they reported all their seizures at each day (i.e. seizure compliance='Y') in the Mate application.

SSF will be calculated for the first 12 weeks, the last 12 weeks, and the 24 weeks of the Maintenance Phase using the seizure data recorded by the investigational wearable watch device, and MATE application from Empatica.

The concordance correlation coefficient (CCC)¹ with 95% confidence interval will be calculated to assess agreement in SSF during the first 12 weeks, the last 12 weeks, and the 24 weeks of the Maintenance Phase between the two Empatica devices and the paper seizure diary.

The concordance correlation coefficient, r_c , for measuring agreement between continuous variables X and Y (both approximately normally distributed), is calculated as follows:

$$r_c = \frac{2S_{XY}}{S_{XX} + S_{YY} + (\bar{X} - \bar{Y})^2}$$

where S_{XX} = variance of X, S_{YY} = variance of Y, S_{XY} = covariance of X and Y.

This is a measure of how well a set of data (Y) compares to a “gold standard” measurement or test (X). It measures both the precision (similar to Pearson’s correlation coefficient), and accuracy (i.e. how far away results are from a 45-degree line through the origin, or from perfect concordance) of the association.

. Similar to the other correlation coefficient, the concordance correlation satisfies $-1 \leq rc \leq +1$. A value of $rc = +1$ corresponds to perfect agreement. A value of $rc = -1$ corresponds to perfect negative agreement, and a value of $rc = 0$ corresponds to no agreement.

Scatter plots of the above SSFs using the seizure data recorded by the watch device as well as Mate application and by those from the paper seizure diary will be presented to evaluate agreement graphically.

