8. SELECTION OF SUBJECTS

8.1. Subject Inclusion Criteria

The subjects who fulfill the following criteria will be included in the study.

1. Male or female subjects \geq 18 years of age.
2. Subject is willing and able to sign informed consent.
3. Subject has a documented diagnosis of epilepsy with simple POS with a motor component or complex POS with or without secondarily generalized seizures as defined in the Classification of Seizures of the International League Against Epilepsy (ILAE, 1981).
4. Subject has a documented electroencephalogram within 10 years prior to screening.
5. Subject has had at least 3 POS during previous six months.
6. Subject has had a sufficient number of seizures at time of enrollment to justify adjunctive therapy, as determined by the Investigator.
7. Subjects are required to be ESL-naïve AND
 - a. Maintained on a stable LEV or LTG regimen for at least 1 month (28 days) prior to screening with no history of adjunctive treatment (for Arm 1, ESL as first add-on).

OR
 - b. Maintained on a stable dose of 1-2 AEDs (excluding OXC) for at least 1 month (28 days) prior to screening and who have had prior adjunctive treatment (for Arm 2, ESL as later add-on).
8. If the subject is treated with any stimulation device for epilepsy (Vagal Nerve Stimulation [VNS], Responsive Neurostimulator [RNS], or similar), the device must have been implanted at least 6 months before screening and the device parameters must be documented as stable for at least 1 month prior to screening. (Note: these devices will not be counted as concomitant AED).
9. Except for epilepsy, subject is judged to be in general good health based on medical history, physical examination findings, and clinical laboratory test results.

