8.2. Subject Exclusion Criteria

1. Subjects with a prior exposure to ESL.
2. Subjects currently being treated with OXC.
3. Subject with a history of allergic reaction to OXC or CBZ, or a history of serious allergic reaction (Stevens-Johnson syndrome, Drug Reaction with Eosinophilia and Systemic Symptoms or similar) to any AED, or a history of serious allergic reactions to other medications.

4. Subjects who have taken warfarin, felbamate, vigabatrin, or perampanel, (unless at stable dose with safety testing for ≥ 1 year) within a 4-week period prior to screening.
5. Subjects taking ezogabine.
6. Subject has taken any medication prohibited for this protocol within 4 weeks prior to Screening (see [Section 10.4](#)).
7. Subjects using benzodiazepines on more than an occasional basis (defined as more than 2 times per week), except when used chronically as an AED (see [exclusion criteria 26](#)).
8. Seizure disorder characterized primarily by simple POS without motor signs.
9. Subject has a history of primarily generalized seizures (eg, myoclonic, absence, tonic).
10. Subject has a history of status epilepticus or cluster seizures (ie, 3 or more seizures within 30 minutes) within the 3 months prior to screening.
11. Subject has had seizures of psychogenic origin or purely subjective seizures within the last 2 years.
12. Subject has had seizures too close to count accurately.
13. Subject has a known progressive structural central nervous system (CNS) lesion, progressive encephalopathy, or a progressive cerebral abnormality.
14. Subject whose current seizures are related to an acute medical illness or other non-epileptic origin.
15. Subjects of Asian ancestry will be excluded if they are carriers of HLA-B*1502. Either:
 - a. Subject must give written informed consent for genotyping, and test negative.

OR

 - b. Subjects must provide documentation of prior testing confirming non-carrier status.

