11.2.2.4. Seizure Diaries

To record seizures during the study, a standardized paper seizure diary and an electronic seizure diary will be dispensed at Visit 1. The subjects will be trained on use of the diaries by the site

personnel. The subjects will also receive a copy of the description of seizure types as presented in the DISCOVER form to ensure that the subject will use correct and consistent terminology to describe the seizures they are experiencing during the study.

The diaries will be completed daily throughout the study, up until the end of the Maintenance Phase (Visit 9, EOS). The diaries require an entry on every day whether a seizure occurs or not. Subjects will record information for each seizure in the paper diary and electronic diary at the same time by date and type of seizure. At each return study visit, the seizure diaries will be reviewed by site staff.

Efficacy evaluations of seizures during the study will be based on the information recorded in the standardized paper daily seizure diary.

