15.3.9. Exploratory Analyses

The proportions of concordance in the daily seizure frequency during the 24-weeks of the Maintenance Phase between the watch device and paper diary as well as between the Mate application and paper diary for each subject will be calculated.

SSF during the first 12 weeks, the last 12 weeks, and the 24 weeks of the Maintenance Phase will be calculated using the seizure data recorded by the investigational wearable watch device, and MATE application from Empatica. The concordance correlation coefficient (CCC) with 95% confidence interval will be calculated to assess agreement in SSF during the first 12 weeks, the last 12 weeks, and the 24 weeks of the Maintenance Phase between the two Empatica devices and the paper diary.

Scatter plots of the above SSFs using the seizure data recorded by the watch device as well as Mate application by those from the paper diary will be presented to evaluate agreement graphically.

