2.3. Exploratory Objectives

The exploratory objectives are

- To evaluate the accuracy of an investigational wearable watch device from Empatica in recording seizure counts.
- To evaluate the performance of an investigational electronic seizure diary in the form of a smartphone application (Empatica MATE).

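### Daily device-diary concordance (SAP 15.4.1) counts days on which both sources record zero, so for low-frequency subjects it says little about whether seizures were detected

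*SAP*

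**What the plan says.** The exploratory objective in SAP 2.3 is "To evaluate the accuracy of an investigational wearable watch device from Empatica in recording seizure counts"; a second objective covers the performance of the MATE electronic diary. Protocol 15.3.9 specifies "The proportions of concordance in the daily seizure frequency during the 24-weeks of the Maintenance Phase between the watch device and paper diary", and the same for MATE, subject by subject. SAP 15.4.1 gives the formula. The numerator counts the days on which device and diary agree on the day's seizure frequency, with no exception for days on which both are zero. That count is then "divided by the number of days with seizure frequency available in paper diary".

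Protocol 11.2.2.4 determines what falls into that denominator: "The diaries require an entry on every day whether a seizure occurs or not". Neither document removes days with zero in both sources or corrects for chance agreement.

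SAP 15.4.1 plans three further items. One is a CCC, reported with its 95% CI, which "will be calculated to assess agreement in SSF during the first 12 weeks, the last 12 weeks, and the 24 weeks of the Maintenance Phase". Scatter plots set device SSF against diary SSF. The MATE concordance is also repeated using only subjects who confirmed that they had reported all their seizures each day. The section contains no detection rate on seizure days and no false-detection rate.

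**The concern.** An accuracy measure should fall when a device misses seizures. Where seizures are rare, this one falls very little, because most of the denominator is made up of days on which there was nothing to detect. It also rises when treatment lowers the seizure rate, even if the device performs exactly as before.

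What is at stake is the reading of the exploratory results. A mean concordance in the nineties could be reported as evidence of accuracy when a device recording nothing would have scored about the same in those subjects. The CCC gives some protection, but it works on totals over 12 or 24 weeks and cannot show whether the device responded on the days the diary records a seizure.

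**Working it through.** The documents state no expected concordance or benchmark, so there is no plan figure to reproduce.

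**Inputs.** The entry minimum is in Protocol 8.1: "Subject has had at least 3 POS during previous six months". Taking six months as 182.5 days, this is 3/182.5 = 0.0164 per day, or 0.46 per 28 days. No numeric maximum is set. Protocol 8.2 excludes a subject under the criterion "Subject has had seizures too close to count accurately", and excludes recent clusters or status epilepticus. All rates above the minimum are therefore assumptions.

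**Step 1: concordance of a device that records nothing.** It matches the diary on exactly the zero-seizure days. With r seizures per 28 days, the expected share of such days is exp(-r/28) if daily counts are Poisson, or 1 - r/28 if there is at most one seizure per day.

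| r per 28 days | Poisson | At most one per day |
|---|---|---|
| 0.46 (entry minimum) | 98.4% | 98.4% |
| 1 (assumed) | 96.5% | 96.4% |
| 2 (assumed) | 93.1% | 92.9% |
| 4 (assumed) | 86.7% | 85.7% |
| 8 (assumed) | 75.2% | 71.4% |
| 28 (assumed) | 36.8% | 0% |

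Clustering of seizures within a subject raises these values. A negative binomial with k from 0.2 to 1 gives 87.5-89.8% at r = 4 and 77.8-83.7% at r = 8.

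**Step 2: dependence on treatment effect.** If treatment halves the rate from 4 to 2 per 28 days, the record-nothing score rises from 86.7% to 93.1% with no change in the device.

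**Step 3: ranking.** At r = 1, a watch with an assumed 90% sensitivity and an assumed 0.1 false detections per day scores 90.2%. The device that records nothing scores 96.5%.

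**Step 4: what the CCC adds.** The SAP formula is r_c = 2·S_XY / (S_XX + S_YY + (mean X - mean Y)²), with X the diary SSF and Y the device SSF.

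- Device that records nothing: Y = 0 for everyone, so S_XY = 0 and r_c = 0. The CCC exposes it.
- Device that misses every seizure but produces the same number of false detections on other days: Y = X for every subject, so S_XY = S_XX = S_YY, the means are equal, and r_c = 1 (given that SSF varies between subjects). With at most one seizure per day, each seizure costs two mismatched days. Daily concordance is then 1 - 2 × 3/182.5 = 96.7% at the entry minimum and 26/28 = 92.9% at r = 1.

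The second device detects nothing, yet does well on both numerical measures in low-rate subjects. It is an extreme case, used only to show that the two measures together do not determine detection.

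**The case against.** The strongest reply is that the plan does not rest on daily concordance alone. A reader might infer that the planned analyses could not tell an accurate device from a silent one. The documents do not support that: a silent device has a CCC of 0, and every device value on the scatter plot would lie at zero. The stated objective also speaks of seizure counts, and the CCC does compare counts.

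Three other strong readings also fail.

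- *Concordance is high whatever the device does.* False detections on seizure-free days lower it directly, as Step 3 shows. The weakness is to missed seizures in low-rate subjects.
- *Nearly all days in this trial will be seizure-free.* Only the 98% figure rests on a documented rate, and that rate is a minimum. Eligibility also requires enough seizures to justify adjunctive therapy, and Arm 2 is described as treatment-resistant, so some subjects may lie well above 4 per 28 days.
- *Days without watch data count as agreement.* SAP 15.4.1 does not say how such days are classed. They could equally be treated as mismatches, and Protocol 11.2.3 refers further detail to a study manual that is not available here.

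For MATE, the repeat analysis in subjects who confirmed complete reporting partly addresses non-entry, although zero-zero days remain in it.

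What stands is narrower. Agreement of period totals does not show that the device responded on the right days, and nothing else in the plan does.

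**Conclusion.** The point holds in a limited form. For subjects at roughly 0.5 to 4 seizures per 28 days, the daily concordance proportion is dominated by zero-zero days and says little about detection, since a device recording nothing would score about 98% down to about 87%. The upper figure follows from the entry criterion. The lower one assumes 4 per 28 days and Poisson daily counts. At higher assumed rates the problem shrinks, with about 75% at 8 per 28 days. The CCC and scatter plots guard against a silent device but not against misses and false detections that offset each other within a period, so day-level accuracy is not measured.

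The consequences are confined to an exploratory, descriptive analysis. Retention is unaffected, and seizure efficacy is taken from the paper diary only.

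**What to change.** Keep the protocol-specified concordance and the CCC. Add to SAP 15.4.1, separately for the watch and for MATE:

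- (a) among diary days with at least one seizure, the proportion with a device-recorded seizure that day;
- (b) among diary seizure-free days, the proportion with a device-recorded seizure, and false detections per 28 days;
- (c) among days on which either source records a seizure, the proportion with matching counts.

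Print the record-nothing value, which is the observed share of seizure-free diary days, beside overall concordance. State how days without watch data are handled, and where recording status is available do not count them as zero-seizure days. The documents do not show whether daily recording status is held, so this part depends on what the device data contain.

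The cost is one extra exploratory table from the same daily data, an entry in SAP 3.4.2 because the measures go beyond Protocol 15.3.9, and agreement figures that will look less favourable. No new data collection is needed for (a) to (c).
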